2.3 Potential Risks and Benefits

2.3.1 Potential Risks

One potential risk relates to the blood draws (e.g., bruising at the site, discomfort, infection) required to obtain the pharmacokinetic samples. All infants should have a long-term indwelling intravenous catheter (e.g. PICC) during hospitalization for administration of IV acyclovir through which blood can be withdrawn without risk of discomfort from a needle stick or bruising at the site during or after the blood drawing and rarely infection. However, once the infant is discharged from the hospital the indwelling intravenous catheter will need to be removed to prevent more harm to the infant as the risk of infection is greater when an indwelling catheter is not being used. Thus, valacyclovir pharmacokinetic samples will need to be obtained via a heel or venous stick on day 2 up to day 7 of valacyclovir therapy. Heel warmers or socks can be used prior to the blood draw to increase blood flow to the heel and reduce the amount of discomfort experienced with squeezing of the infant's heel in order to obtain the amount of blood necessary. The weight-based volumes required for the study-specific procedures are less than the limits of the Institutional Review Board and the NIH.

Additionally, daily random pharmacokinetic samples obtained during the first week of IV acyclovir will be obtained only at the time of clinical blood draws (creatinine and/or CBC/diff) to prevent additional venipuncture procedures solely for study purposes. The weight-based volumes required for the study-specific procedures are less than the limits of the Institutional Review Board and the NIH.

Potential risks associated with the use of valacyclovir are comparable to the risks associated with long term use of the current standard of care, oral acyclovir. Therefore, monitoring for adverse events is not necessary for short term use (2 and up to 7 days) of valacyclovir.

2.3.2 Known Potential Benefits

Knowledge of the pharmacokinetic profile will aid in determining if 20 mg/kg/dose every 8 hours is the most appropriate dose of valacyclovir to be used in infants (≤ 84 days of age) for treatment of neonatal SEM HSV disease. It will also provide further baseline information for future studies to evaluate the use of valacyclovir in infants with neonatal HSV CNS disease. This information can aid in decreasing the length of hospitalization, emotional burden on families, and ultimately health care costs. Participants will not directly benefit themselves from participating, though.

3 OBJECTIVES

3.1 Study Objectives

Primary:

- To define the pharmacokinetics of valacyclovir in neonates (\geq 34 weeks gestational age at birth and \geq 2000 g)
- To assess safety of valacyclovir administration

Secondary:

- To assess the pharmacokinetics of high-dose parenteral acyclovir in neonates \geq 34 weeks gestation with virologically confirmed neonatal HSV disease who are receiving acyclovir as standard of care
- To compare the pharmacokinetics of high-dose parenteral acyclovir to the pharmacokinetics of the proposed study dose of valacyclovir (20 mg/kg every 8 hours)

3.2 Study Outcome Measures

3.2.1 Primary Outcome Measures

Primary Endpoint:

- Plasma pharmacokinetic parameters for valacyclovir AUC_8
- Cumulative incidence of Grade 3 or higher unsolicited adverse events, serious adverse events, or any adverse event that is not recovered / not resolved

3.2.2 Secondary Outcome Measures

Secondary Endpoints:

- Plasma pharmacokinetic parameters for parenteral acyclovir AUC_8
- Comparison of AUC_8 of 20 mg/kg IV acyclovir to the AUC_8 of 20 mg/kg PO valacyclovir

4 STUDY DESIGN

This study is an open-label, single-center, pharmacokinetic study of valacyclovir pharmacokinetics in male and female infants \geq 34 weeks gestation, \leq 42 days of age at initiation of intravenous acyclovir, and \geq 2000 g who have been diagnosed with virologically confirmed neonatal HSV disease via culture or polymerase chain reaction (PCR). Infants who meet the inclusion criteria will be eligible for the study, and informed consent will be obtained by the infant's parent(s) or legal guardian(s).

Subjects meeting enrollment criteria will be enrolled in this clinical trial. The total sample size will be 6 and up to 10 infants diagnosed with any of the 3 disease classifications of neonatal HSV disease. Following enrollment, infants during the first week of treatment with intravenous acyclovir as per standard of care will have daily random pharmacokinetic levels (population based pharmacokinetics) obtained at the same time of clinical blood draws (e.g. creatinine and/or CBC/diff), namely using remnant specimens. During the second week of treatment with IV acyclovir (between dose 22 and 42) infants will have one pharmacokinetic sampling profile obtained. The plasma specimens for the pharmacokinetic sampling profile will be drawn immediately prior to next dose (within 30 minutes prior to the start of infusion and 8 hours after previous dose) for an 8 hour trough, a post-infusion peak obtained within 15 minutes following completion of infusion, and 3-4 hours after infusion. Once these samples are obtained, the infant will complete the course of IV acyclovir per the standard of care guidelines.

Upon completion of the intravenous acyclovir per standard of care, the infant will be switched to valacyclovir 20 mg/kg every 8 hours for 2 and up to 7 days depending upon availability of the CHRU. The first dose of valacyclovir is to be given 8 hours after completion of the last dose of IV acyclovir. On day 2 (up to 7), the infant will return to UAB's CHRU for a PK profile to be obtained. The plasma specimens for the pharmacokinetic profile will be drawn at hour 0 (just prior to the scheduled valacyclovir dose and 8 hours after the last dose), at 1-2 hours after dose for a peak level, and 3-5 hours after dose. Once the infant completes the pharmacokinetic sampling, the infant will have completed the study and will be switched to oral acyclovir per standard of care guidelines to complete 6 months of oral suppressive therapy for neonatal HSV disease. The parent(s) or guardian will be instructed to have the infant follow with an infectious disease specialist for appropriate follow up of neonatal HSV disease while on suppressive therapy.

All participants will receive the standard of care treatment with 14 to 21 days of IV acyclovir (depending on disease classification) followed by 6 months of oral antiviral suppression. The only change is that the first few days of oral suppression will be with valacyclovir instead of acyclovir. Subjects with inadequate pharmacokinetic data for analysis (e.g., due to dropping out of the study before PK assessments are performed or blood sampling obtained but is

inadequate for analysis) may be replaced and will not count toward the total of 6 and up to 10 subjects.

Treatment Day 1 is the calendar day when the first dose of parenteral acyclovir was administered to the study subject for clinical purposes and will be the date against which follow-up visits will be defined. **Treatment Dose 1** corresponds to the first dose of parenteral acyclovir given to the study subject for clinical purposes. The study enrollment day is unlikely to be the same day as Treatment day 1 as individuals will need confirmation of neonatal HSV infection in order to be enrolled. Participants can enroll on or before treatment day 14. **Study Assessment Day 1** is the calendar day when the participant is enrolled in the study.

The study will be divided up into 3 periods: **Period 1** will consist of **Treatment Day 1 through Treatment Day 7**, **Period 2** will consist of **Treatment Day 8 through Treatment Day 14 (or 21 if being treated for CNS or disseminated infection)**, and **Period 3** will be from the initiation of valacyclovir (started after completion of IV acyclovir) until the collection of PK valacyclovir specimens. Although it is anticipated, but not required, that patients are enrolled in the study prior to treatment day 7 in order to participate in all 3 periods, all patients will be enrolled on or before treatment day 14 and will be included in all eligible periods based on pre-determined classification.

During **Period 1**, daily pharmacokinetic specimens will be obtained randomly but only at times of other clinical blood draws. The acyclovir dose, time of last acyclovir infusion prior to blood draw, and time of blood draw will be recorded. During **Period 2**, only one pharmacokinetic sampling profile will be obtained between **Treatment Dose 22 and Treatment Dose 42**. The pharmacokinetic specimens for the profile will be obtained at hour 0 (within 30 minutes of the next parenteral acyclovir dose), within 15 minutes of completion of parenteral acyclovir infusion, and 3-4 hours after infusion.

During **Period 3**, a pharmacokinetic sampling profile will be obtained while the infant is on valacyclovir. Pharmacokinetic specimens will be obtained at hour 0 (immediately prior to next valacyclovir dose; window: -15 min), 1-2 hours post dose, and 3-5 hours post dose. Valacyclovir dose, date, time of last valacyclovir dose, and time of blood draw will be recorded.

All pharmacokinetic specimens will be taken to the UAB Antiviral Pharmacology Laboratory for processing. No additional blood samples will be required for research purposes.

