9.1 Safety Reporting: Adverse Events of Special Interest (AESI)

The investigator must also report the following AESI on the AESI case report form:

- AEs associated with blood draws
- All adverse events that meet the reporting requirements of the Institutional Review Board (which will also be reported to Protocol Chair).

The risks associated with participation in the clinical trial are associated with blood draws and potential side effects to valacyclovir. However, the potential drug risks for valacyclovir are comparable to the risks associated with long term use of the current standard of care, oral acyclovir. Therefore, monitoring for adverse events is not necessary for short term use (2 and up to 7 days) of valacyclovir. In an effort to document only untoward medical events that have a greater likelihood of being study-related, only adverse events associated with blood draws will be considered adverse events for the purposes of this protocol.

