9.2 Type and Duration of Follow-up of Subjects after Adverse Events

All AEs as described above will be followed until resolved or considered stable.

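### No study contact follows the last valacyclovir PK draw, so later blood-draw events are not actively sought, and the primary safety endpoint gives no time for judging non-resolution

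*Combined protocol and SAP*

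**What the plan says.** **End of observation.** Section 4 closes the study for each infant at the valacyclovir PK visit: "Once the infant completes the pharmacokinetic sampling, the infant will have completed the study and will be switched to oral acyclovir". The same section runs Period 3 from the start of valacyclovir "until the collection of PK valacyclovir specimens". In Appendix A the valacyclovir PK visit is the last column.

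**Where the sticks fall.** Sections 7.3.1 and 7.3.2 take the intravenous acyclovir samples at clinical draws or through the indwelling catheter, with no venipuncture solely for the study. Sections 2.3.1 and 7.3.3 take the valacyclovir samples by heel or venous stick. Section 2.3.1 names the hazards: "One potential risk relates to the blood draws (e.g., bruising at the site, discomfort, infection".

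**What counts as an adverse event.** Section 9.1 states that "only adverse events associated with blood draws will be considered adverse events for the purposes of this protocol". It also asks for "All adverse events that meet the reporting requirements of the Institutional Review Board", with no time limit given.

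**Endpoint and follow-up.** Section 3.2.1 makes the cumulative incidence of three kinds of event a primary endpoint: unsolicited events of Grade 3 or higher, serious events, and "any adverse event that is not recovered / not resolved". Section 9.2 says "All AEs as described above will be followed until resolved or considered stable". Section 7.4 applies Section 9 follow-up after early withdrawal as well.

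**The concern.** Blood-draw events are the main kind of adverse event this protocol recognises, and the draws that need a study-only stick all come in the last hours of participation. Two of the named hazards, infection and bruising, may first become apparent after the infant has gone home, and nothing in the schedule would then ask about them. A report of no stick-site infections would partly reflect when observation stopped.

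The second problem is one of definition. The non-resolution component applies at any grade, so whether a mild event enters a primary endpoint depends only on whether it is judged resolved. The plan does not say when that judgement is made. Two analysts could apply the text in good faith and classify the same infant differently.

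**Working it through.** **1. Plan's own figure.** There is none to reproduce. Section 11.2 sets the sample at 6 to 10 on experience, feasibility and expected low kinetic variability. Section 11.4 offers counts and proportions for categorical variables, with no precision target for the safety endpoint.

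**2. Scheduled observation after each stick.** Inputs from Section 7.3.3: draws at 0 h (up to 15 minutes before the dose), 1-2 h and 3-5 h after the dose. Participation ends at the third draw.

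| Stick | Time to end of participation |
|---|---|
| First (0 h) | 3-5 h, plus up to 15 minutes |
| Second (1-2 h) | 3 - 2 = 1 h to 5 - 1 = 4 h |
| Third (3-5 h) | 0 h |

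**3. Could another provision find a new event after that?**
- Section 9.2 covers events already identified. No visit or call is scheduled to carry it out.
- Sections 9 and 9.1 require reporting of IRB-reportable events, and Section 14.2 requires the IRB to be told of significant ones. The site must first hear of them.
- Section 4 directs families to an infectious disease specialist. No date is fixed and no study data collection is stated.
- Section 7.5 has unscheduled visits assessed as standard of care.

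All of these are passive. None is a planned enquiry about new events.

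**4. When is non-resolution judged?** Take an infant with a mild blood-draw event present at the third draw.
- Judged at study completion (Section 4), it is unresolved and counts under Section 3.2.1.
- Followed to resolution (Section 9.2), it does not count.
- Followed until stable but still present (Section 9.2), follow-up closes and Section 3.2.1 does not say how to score it.

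**5. Weight of one infant.** The change in incidence is 1/n: 1/6 = 16.7 percentage points, and 1/10 = 10 points.

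**6. What a zero would show even with complete ascertainment.** The one-sided 95% upper bound for zero events is 1 - 0.05^(1/n):
- n=6: 1 - 0.05^(1/6) = 39.3%
- n=10: 1 - 0.05^(1/10) = 25.9%

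These bounds assume that every event would be found. Without a contact after the last stick, that assumption is not secured for late events.

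**The case against.** The strongest reply is that Sections 4 and 9.2 are compatible. One ends study procedures, while the other continues follow-up of any known adverse event; Section 7.4 shows that follow-up is meant to outlast participation. On that reading an event seen at the visit is followed and, once resolved, is not counted. This stands, and it disposes of three stronger readings that a reader might infer.

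- *A fresh bruise at the last draw is automatically a primary endpoint event.* No section fixes scoring at that moment, and Section 9.2 points the other way. What remains is an unstated assessment time and the unsettled status of events closed as stable. The documents give no bruising rate, so no expected count of such events can be put forward.
- *Late events cannot be seen at all.* IRB-reportable events have no stated time limit, and families are referred to a specialist. The accurate statement is that late events are not actively sought.
- *The early close is why effects of the last valacyclovir doses are missed.* Sections 2.3.1 and 9.1 drop adverse-event monitoring for the whole of the valacyclovir course, so a longer window alone would not capture drug effects. That depends on reconciling Section 9.1 with the safety objective in Section 3.1 and the endpoint in Section 3.2.1, which is a separate matter.

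It can also be said that three draws of 0.2 mL in 6-10 infants carry little risk. That may be so, but the plan made the incidence a primary endpoint, and the means of ascertaining it should match.

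**Conclusion.** The point holds in two limited parts. First, there is no active ascertainment of blood-draw events that begin after the PK visit, and scheduled observation after the three study sticks is about 5 h at most and 0 h for the last. Second, the non-resolution component has no assessment time and no rule for events closed as stable, so one infant's classification, worth 16.7 points at n=6 or 10 points at n=10, can depend on which section is applied.

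The first part rests on Appendix A and Section 7.3.3 being the full schedule, and on some stick effects becoming apparent only later. The second needs only one adverse event that is open at the last draw or later closed as stable. How often either would occur cannot be estimated from the documents. The pharmacokinetic endpoints are not affected. This is a cheap improvement worth making, not a flaw that prevents the study from meeting its main aim.

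**What to change.** 1. Add one scripted telephone contact with the parent at a fixed time after the last PK draw, made by existing staff. State the time and its window in advance, chosen to cover when stick-site infection or bruising would be expected to show. List it in Appendix A and in Section 9.2.
2. State in Section 3.2.1 that new blood-draw events up to that contact count towards the endpoint.
3. Define non-resolution in Section 3.2.1 as the event's final outcome when Section 9.2 follow-up closes, and say how an event closed as stable is scored. Scoring by status at the call would only move the problem, because an event starting shortly before it would still be open.
4. Reword Section 4 so that the PK visit ends sampling and the call ends the planned search for new events.
5. Update the 26-day maximum participation in the Protocol Summary. Counted from Treatment Day 1, the present schedule already gives 14 + 7 = 21 days for SEM disease and 21 + 7 = 28 days for CNS or disseminated disease. The call adds to these.

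The cost is 6-10 calls, an IRB amendment and slightly longer participation, with no added visit or blood draw and no change to treatment.

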5 STUDY ENROLLMENT AND WITHDRAWAL

Male and female infants \geq 34 weeks gestation of any ethnicity with virologically confirmed neonatal HSV disease via culture- or polymerase chain reaction (PCR). The study population will be drawn from the in-hospital setting. Potential subjects will be identified by the site investigators and the study coordinators. Patients meeting study eligibility criteria will be offered enrollment into the trial. Informed consent signed by study subject's parent(s) or guardian(s) must be obtained prior to study enrollment. Site investigators are all clinicians who have direct access to the study population.

5.1 Subject Inclusion Criteria

1. Signed informed consent from parent(s) or legal guardian(s)
2. Confirmation of HSV infection from surface culture/PCR, skin lesion culture/PCR, blood PCR, or CSF PCR (performed at UAB Virology lab)
3. \geq 34 weeks gestational age at birth
4. Weight at study enrollment is \geq 2000 grams
5. Receiving intravenous acyclovir, prescribed by the patient's physician for \leq 14 days
6. \leq 42 days of age at initiation of parenteral acyclovir
7. Creatinine \leq 1.2

5.2 Subject Exclusion Criteria

1. Imminent demise
2. Current receipt of other investigational drugs
3. Major congenital anomaly that in the site investigator's opinion may impact drug metabolism or the patient's volume of distribution
4. Creatinine of > 1.2 prior to initiation of valacyclovir
5. Evidence of immunosuppression (HIV infected, immune deficiencies, etc.)
6. Any condition that, in the opinion of the investigator, would place the subject at an unacceptable injury risk or that may interfere with successful study completion
7. > 42 days of age at initiation of parenteral acyclovir
8. Concern for parental/guardian compliance

5.3 Treatment Assignment Procedures

5.3.1 Randomization Procedures

Since this is a pharmacokinetic sampling study evaluating valacyclovir with no therapeutic intervention or investigation, no randomization procedures are required.

5.3.2 Reasons for Delaying Study-Related Procedures

Study related laboratory draws will be delayed or deferred if the investigator believes that obtaining them might increase subject risk. If a study related laboratory draw is delayed or deferred, study staff will document this on a source document.

5.3.3 Reasons for Withdrawal

The criteria for discontinuations during the study include:

- Study subject (parent/legal guardian) wishes to withdraw
- An alternate cause of disease (bacterial or other viral) is identified and acyclovir is discontinued
- Non-compliance with study procedures
- Trial termination (by UAB, or agreement of all investigators)
- Any other reason which, in the opinion of the investigator, precludes the study subject's participation in the study. The principal investigator must call the Protocol Chair prior to discontinuing a study subject for this reason.

5.3.4 Handling of Withdrawals

Study subjects may withdraw voluntarily from participation in the study at any time. If a study subject withdraws or is discontinued from the study at any time prior to completion of the study, the reason for this decision will be recorded on the eCRFs. If subject withdraws before collection of the pharmacokinetic collection, this subject may be replaced (see Section 4).

5.3.5 Termination of Study

The PI and study team have the right to terminate this study at any time. Reasons for terminating the study may include, but are not limited to, the following:

- Study subject enrollment is unsatisfactory
- Data recording is inaccurate or incomplete
- Investigators do not adhere to the protocol or applicable regulatory guidelines in conducting the study.

6 STUDY INTERVENTION/INVESTIGATIONAL PRODUCT

Although valacyclovir does not currently have a recommended dose for infants 2 months and younger, this study is mainly a pharmacokinetic sampling study of valacyclovir in infants 2 months and younger and is not being used for a therapeutic intervention. Currently intravenous acyclovir is recommended for treatment of neonatal HSV disease, which these infants will receive per standard of care guidelines. The infants will only receive a short course of valacyclovir (2 and up to 7 days) in order to obtain the pharmacokinetic profile and then will be switched to the standard of care oral acyclovir to complete 6 months of suppressive therapy. The only change is that the first few days of oral suppression will be with valacyclovir instead of acyclovir.

6.1 6.1. Study Product Description

6.1.1 Acquisition

Valacyclovir will be resourced from COA's wholesaler.

6.1.2. Formulation, Packaging, and Labeling

A pharmaceutically-manufactured liquid formulation of valacyclovir does not exist at this time, but the American Society of Health-System Pharmacists provides instructions on how to make an extemporaneous preparation of oral suspension from 500 mg caplets. COA's Investigational Drug Pharmacy will prepare, package, and label the study medication. Valacyclovir is supplied in amber glass medicine bottles. It will be labeled as an investigational product.

